10.4 Study Center File Management

It will be the responsibility of the Principal Investigator to assure that the study file at the center is maintained. The study file for this protocol will contain, but will not be limited to, the information listed below:

- Investigator's Brochure (all versions provided during the study period.)
- Final study protocol.
- Protocol amendments (if applicable).
- Original informed consent form (blank).
- Revised informed consent forms and/or all addenda (if applicable).
- Copy of signed FDA Form(s) 1572
- Curricula Vitae and medical licenses of Principal Investigator and Subinvestigators.
- Financial Disclosure Form of Principal Investigator and Subinvestigators (if applicable).
- DHHS Number for IRB, or other documentation of IRB compliance with FDA regulation (US sites).
- Documentation of IRB/IEC approval of protocol, consent form, any protocol amendments and any consent form revisions.
- Annual IRB/IEC updates and approvals.
- All correspondence between the Principal Investigator, IRB/IEC and Sponsor or Sponsor's representative relating to study conduct.
- Copies of all 7-day and 15-day Safety Reports submitted to the Regulatory Authorities (provided by Sponsor) and IRB/IEC correspondence documenting their submission.
- Laboratory certifications.
- Normal laboratory value ranges for tests required by the protocol for all laboratories that are utilized.
- CRA monitoring log.
- List of signatures and Delegation of Authority for all study personnel
- Drug invoices for both receipt and return of study drug, as well as drug inventory/accountability records.

11. STATISTICAL ANALYSIS

A brief overview of the statistical analysis plan is presented below. Complete details of the planned analysis will be documented in a full Statistical Analysis Plan, which will be finalized before locking the study database.

11.1 Statistical Methods

Statistical analyses will be performed using Statistical Analysis System (SAS) software. Default estimation methods in version 9.4 of SAS are always used unless an alternative is specified below. In general, data summaries will include the mean, standard deviation, median, minimum and maximum values for continuous data; the median, 25th and 75th percentiles, minimum and maximum values for time-to-event endpoints; and the number and percentage of patients in each category for categorical data. Pointwise 95% confidence intervals (CI) will also be estimated for the mean (continuous data), median (time-to-event endpoints) or percentage of patients (categorical data).

Durations of time expressed in months (eg, times-to-event endpoints) will be reported in proportional “months” according to the formula

$$months = \frac{12}{365} \times days$$

Baseline value of a characteristic is defined as the last measured value prior to the first dose of study drug.

Statistical p-values will be truncated for display at the third digit following the decimal point. P-values less than 0.001 will be displayed as “<0.001.”

11.2 Sample Size

11.2.1 Sample Size in Stage 1

The sample size of 23 eligible patients for Stage 1 was selected because it allows estimation of the remission rate by means of a 90% confidence interval with maximum width of ±17%. Although this study does not follow a Simon 2-stage design, 23 patients is consistent with the sample size for Stage 1 of the Simon 2-stage minimax design with 80% power for testing the null hypothesis that the remission rate is 50% against a one-sided alternative at the 5% level of significance when the actual remission rate is 70%. In the Simon 2-stage design described, the study would continue to Stage 2 only if 13 patients achieve remission out of a maximum of 23 eligible patients. Therefore, this was selected as the requirement to proceed to Stage 2 of this study. However, the study may proceed to Stage 2 as soon as 13 patients achieve remission.

The primary objective of Stage 1 is to determine the CR rate in patients with relapsed or refractory AML with MCL-1 dependence of $\geq 30\%$. Thus a patient who leaves the study prior to providing a bone marrow sample adequate for assessing response to treatment will be replaced by another eligible patient.

11.2.2 Sample Size in Stage 2

The planned sample size of 56 patients (28 per treatment arm) in Stage 2 of this study provides 90% power to reject the null hypothesis of equal CR rates across treatment arms under the following conditions:

- CR rates of 70% and 30% for patients receiving ACM and CM, respectively
- One-sided 2.5% significance level
- Randomization based on a 1:1 patient allocation ratio (ACM to CM)

The primary objective of Stage 2 is to compare CR rates between patients with relapsed or refractory AML with MCL-1 dependence of $\geq 30\%$ receiving 1 cycle of ACM treatment and those receiving 1 cycle of CM. Thus a patient who leaves the study prior to receiving one course of study treatment will be replaced by another eligible patient.

11.3 Analysis Populations

- **Intent-to-treat (ITT) patient population:** includes all patients enrolled into Stage 1; the exploratory arms; or randomized to receive study drug in Stage 2 regardless of whether they actually received study drug and regardless of whether evidence is found indicating they failed to meet study inclusion/exclusion criteria or had other protocol violations. When the ITT patient population is analyzed, Stage 2 patients are grouped according to their randomized treatment regardless of actual treatment received. The ITT patient population is the analysis population for all primary statistical inference and tests of hypotheses related to efficacy endpoints.
- **Safety patient population:** a subset of ITT patients who received at least one dose of study drug. When the safety patient population is analyzed, patients are grouped according to actual treatment received. ACM is considered a patient's "treatment received" in the safety patient population if alvocidib is administered at any time during the study. The safety patient population is the analysis population for all analyses of safety data.
- **Per-protocol patient population:** a subset of the safety patient population who either (a) have at least one response evaluation on study, or (b) die prior to their first scheduled response evaluation. However, patients are excluded from the per-protocol patient population if they have

an important protocol deviation, such as when evidence is found indicating they failed to meet any study inclusion/exclusion criterion. When the per-protocol patient population is analyzed, patients are grouped according to actual treatment received. ACM is considered a patient's "treatment received" in the per-protocol patient population if alvocidib is administered at any time prior to CR (or at any time during the study for patients never achieving CR). The per-protocol population is used for sensitivity (secondary, supportive) analyses of efficacy endpoints.

- **Response-assessment population:** a subset of the safety population who have at least one response evaluation on study. When the response-assessment patient population is analyzed, patients are grouped according to actual treatment received. ACM is considered a patient's "treatment received" in the response assessment patient population if alvocidib is administered at any time prior to CR (or at any time during the study for patients never achieving CR). The response-assessment population is the primary population for assessing the correlation between MCL-1 dependency and response to ACM and is used for sensitivity (secondary, supportive) analyses of efficacy endpoints.

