Patients not demonstrating evidence of CR, CRi, CRp, or PR after the first cycle of treatment will be considered for removal from the study, although with permission of the Medical Monitor, induction treatment may continue, if clinically indicated, and provided there is no evidence of toxicity ≥NCI CTCAE grade 4 (v4.03 in Stage 1, v5.0 in Stage 2; see [Appendix C](#)). This study also includes a crossover option for those randomized to CM (see below).

- Crossover: Patients randomized to CM with progressive disease or no response after 1 cycle of CM may cross over to receive ACM. In addition, patients randomized to CM with the best response of a PR after 2 cycles of CM may also cross over to receive ACM. Patients who cross over to ACM may receive up to a combined total (CM + ACM) of 4 cycles. Patients crossing over who meet the above criteria (lifetime daunorubicin equivalent exceeds 460 mg/m² or the LVEF drops below 45%) will receive only AC (alvocidib and cytarabine) for all cycles instead of ACM.

Complete remission rates will be compared across treatment groups using the Cochran-Mantel-Haenszel general association test stratified by response to most recent induction therapy. The same test will be applied to assess the statistical significance of the secondary response rate endpoints.

Incidence rates of treatment-emergent adverse events (TEAEs) will be summarized within treatment group at the Medical Dictionary for Regulatory Activities (MedDRA) preferred term and primary system organ class levels. Similar summaries will be made for subsets of adverse events (AEs) such as (1) those judged by the Investigator to be related to study treatment, and (2) serious adverse events (SAEs).

Other routine safety assessments (eg, clinical laboratory parameters and vital signs) will be summarized by treatment group using mean, standard deviation, median, minimum and maximum changes from baseline values.

The study is expected to take 20-24 months to enroll up to 137 patients: 25 patients in Stage 1; 56 patients in the 4 Exploratory Arms (closed after Amendment 8); and 56 patients (28 patients in each of two treatment arms) in Stage 2.

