7.2 Safety Endpoints

Tolerance and toxicity of the ACM versus CM regimens will be assessed through evaluation of physical examinations, vital signs, laboratory studies, solicited and unsolicited adverse events, and all causes of mortality at 30 and 60 days.

- 30- and 60-day Mortality
- Adverse Events
- Clinical Laboratory Assessments

A Data Safety Monitoring Board (DSMB) will monitor key outcomes from the study.

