11.4.4 Safety Analyses

The following safety analyses will be performed on all patients who receive at least one dose of study drug.

- **30- and 60-day Mortality** = Estimates of 30- and 60-day mortality and their pointwise 95% CIs will be derived from Kaplan-Meier curves for OS by treatment arm
- **Adverse Events** = Reported AE terms will be mapped to MedDRA preferred terminology. All reported events will appear in AE listings, however only TEAEs will be summarized. A TEAE is an AE that starts or increases in severity any time after the first administration of any study drug up to 30 days following the last administration of any study drug. AE severity will be rated by the investigator according to NCI CTCAE version 4.03 in Stage 1 and version 5.0 in Stage 2 (see *Appendix C*).
- **Clinical Laboratory Assessments** = Laboratory test results measured on a continuous scale and changes from baseline values will be summarized by visit and within treatment arm using mean, standard deviation, median, minimum and maximum values. Categorical test results will be summarized within treatment arm using shift tables. Additionally, for tests where NCI CTCAE, version 4.03 in Stage 1 and version 5.0 in Stage 2 (see *Appendix C*), severity criteria are specified, NCI CTCAE severity grades will be summarized in shift tables.
- **Vital Signs** = Vital signs and changes from baseline values will be summarized by visit and within treatment arm using mean, standard deviation, median, minimum and maximum values.

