List of Appendices

Appendix 1. Criteria for Grading Severity of Clinical Tumor Lysis Syndrome.....	33
Appendix 2. Sample Summary Table Templates	34

1. Synopsis

Protocol Title:

A Phase 2, Randomized, Biomarker-Driven, Clinical Study in Patients with Relapsed or Refractory Acute Myeloid Leukemia (AML) with an Exploratory Arm in Patients with Newly Diagnosed High-Risk AML and Exploratory Arms with Varying Levels of MCL-1 Dependence

Study Design:

There is a primary study component and four exploratory study arms

- Primary Study: single-arm, Simon two-stage lead in to confirm efficacy assumptions followed by a randomized, two-arm parallel design
- Exploratory Study Arms: single-arm observational

Study Populations:

- Primary Study: Relapsed and refractory AML patients with MCL-1 dependence $\geq 40\%$
- Exploratory Study Arms:
 - Patients with newly diagnosed, high-risk AML and MCL-1 dependence $\geq 40\%$
 - Relapsed and refractory AML patients with MCL-1 dependence between 0% and $< 15\%$
 - Relapsed and refractory AML patients with MCL-1 dependence between 15% and $< 30\%$
 - Relapsed and refractory AML patients with MCL-1 dependence between 30% and $< 40\%$

Treatment Arms:

- ACM (alvocidib, Ara-C [cytarabine] and mitoxantrone)
- CM (Ara-C [cytarabine] and mitoxantrone)

Biomarker:

- MCL-1 dependence measured by mitochondrial sensitivity to NOXA BH3 peptides (hereafter referred to as MCL-1 dependence)

Sample Size:

- Primary Study, Stage 1: up to 23 patients
- Primary Study, Stage 2: 106 patients (53 patients per treatment arm)
- Exploratory Study Arms: 20 patients in each of four exploratory patient populations

Randomization:

- Primary Study, Stage 1: Not randomized, all patients receive ACM

- Primary Study, Stage 2: Randomized 1:1 to ACM or CM stratified by response to frontline AML therapy
- Exploratory Study Arms: Not randomized, all patients receive ACM

Analysis Populations:

Intent-to-treat (primary for efficacy), safety, response-available, per-protocol, crossover

Response Assessments:

Central review performed by a panel of independent, expert hematologists according to an approved charter under change control (primary response assessment); local review of bone marrow and blood test results by the investigator at the study center where patient is enrolled (secondary assessment); “sponsor review” by employees and/or agents of Tolero Pharmaceuticals

Missing Values:

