7.1. Analysis Populations

The intent-to-treat (ITT) patient population includes all patients randomized to receive study drug regardless of whether they actually received study drug and regardless of whether evidence is found indicating they failed to meet study inclusion/exclusion criteria or had other protocol violations. When the ITT patient population is analyzed, patients are grouped according to their randomized treatment regardless of actual treatment received. The ITT patient population is the analysis population for the primary analyses of efficacy endpoints (i.e., all statistical inference and tests of hypotheses related to efficacy endpoints in stage 2 and univariate summaries of efficacy endpoints in stage 1 and the exploratory study arms).

The safety patient population is the subset of ITT patients who received at least one dose of study drug. When the safety patient population is analyzed, patients are grouped according to actual treatment received. ACM is considered a patient’s “treatment received” in the safety patient population if alvocidib is administered at any time during the study (except for ACM administered to a “crossover” patient). The safety patient population is the analysis population for all analyses of safety data.

The response-available patient population is the subset of safety patients who have at least one response assessment on study. However, patients are excluded from the response-available patient population if they have an important protocol deviation, such as when evidence is found indicating they failed to meet any study inclusion/exclusion criterion. When the response-available patient population is analyzed, patients are grouped according to actual treatment received. ACM is considered a patient’s “treatment received” in the response-available patient population if alvocidib is administered at any time prior to a combined remission or at any time during the study for patients never achieving combined remission (except for ACM administered to a “crossover” patient). The response-available population is used for biomarker analyses and sensitivity (secondary, supportive) analyses of efficacy endpoints.

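### The protocol's safety set puts never-randomised Stage 1 and exploratory-arm patients, and CM patients who cross over, in the ACM group, with no limit to Stage 2 for the ACM-versus-CM safety summaries

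*Protocol*

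**What the plan says.** **Protocol 11.3.** The ITT set "includes all patients enrolled into Stage 1; the exploratory arms; or randomized to receive study drug in Stage 2". The safety set is the part of ITT that received at least one dose. It is grouped by treatment received, and alvocidib at any point in the study makes a patient ACM. The section adds: "The safety patient population is the analysis population for all analyses of safety data".

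**Protocol 11.4.4.** "The following safety analyses will be performed on all patients who receive at least one dose of study drug". Mortality, laboratory and vital-sign summaries are by treatment arm. Adverse events are graded by CTCAE 4.03 in Stage 1 and 5.0 in Stage 2.

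**Protocol 7.2.** "Tolerance and toxicity of the ACM versus CM regimens will be assessed".

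**Protocol 11.4.** Primary efficacy comparisons use Stage 2 data only. No such sentence exists for safety.

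**SAP 1 (Synopsis).** Stage 1 and all four exploratory arms are non-randomised and receive ACM. One exploratory arm is "Patients with newly diagnosed, high-risk AML and MCL-1 dependence" of at least 40%. The others are relapsed/refractory AML with MCL-1 dependence of 0 to <15%, 15 to <30% and 30 to <40%.

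**SAP 7.1.** The ITT set "includes all patients randomized to receive study drug regardless of whether they actually received study drug". The same paragraph nevertheless uses ITT for univariate efficacy summaries in Stage 1 and the exploratory arms. Alvocidib given to a crossover patient does not make that patient ACM in the safety set.

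**MCL-1.** Protocol 11.3 says: "The response-assessment population is the primary population for assessing the correlation between MCL-1 dependency and response to ACM". Protocol 11.4.3 fits MCL-1, arm and their interaction, and gives an AUC by arm. SAP 7.10 leaves CM and newly diagnosed patients out of its MCL-1 model and AUC.

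**The concern.** Stage 2 is the only randomised source of evidence on what alvocidib adds in toxicity to cytarabine and mitoxantrone. Read as written, the safety definitions put that evidence into an ACM group drawn mostly from other cohorts, while CM contains Stage 2 patients only. A difference between the two columns would then mix the effect of alvocidib with differences in disease setting, MCL-1 range, enrolment period and grading version. It could hide a real excess or create a false one, and a reader of the pooled table could not tell which.

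Crossover adds a second problem. A CM patient must survive to the cycle 1 response assessment before crossing over. Moving such patients to ACM takes survivors out of CM and leaves its early deaths behind, and it credits to ACM events that happened on CM.

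**Working it through.** **1. The plan's own total.** Protocol 4.1 and 4.4.1 give 25 in Stage 1, 56 in the exploratory arms and 28 per arm in Stage 2. 25 + 56 + 28 + 28 = 137, as stated.

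**2. The 11.3 rule applied to those counts** (everyone dosed, no crossover).
- ACM = 25 + 56 + 28 = 109; CM = 28; ratio 109/28 = 3.9.
- Never randomised within ACM = 25 + 56 = 81; 81/109 = 74.3%.
- At the SAP's older planned counts: ACM = 23 + 4×20 + 53 = 156 against 53. Never randomised = 103/156 = 66%. The problem does not depend on which document's counts are used.

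**3. Weight of the randomised contrast.** Let a and c be the Stage 2 event rates on ACM and CM, and n the rate in the 81 others.

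Displayed difference = (28a + 81n)/109 − c = 0.257(a − c) + 0.743(n − c).

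The randomised difference gets about a quarter of the weight. Illustrations with assumed rates (the documents give none for these cohorts):

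| a | c | n | Pooled ACM | Displayed difference | Randomised difference |
|---|---|---|---|---|---|
| 10% | 10% | 5% | (2.8 + 4.05)/109 = 6.3% | −3.7 points | 0 |
| 10% | 10% | 20% | (2.8 + 16.2)/109 = 17.4% | +7.4 points | 0 |
| 25% | 10% | 10% | (7 + 8.1)/109 = 13.9% | +3.9 points | +15 points |

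If n equals the common Stage 2 rate, there is no distortion. The sign depends on n, which is unknown.

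**4. Crossover under the protocol's rule.** Take the planned CM CR rate of 30%, so that 0.70 × 28 ≈ 20 patients lack CR. This is an upper bound on crossover, because not every such patient qualifies. If 25%, 50% or 100% of them cross over, 5, 10 or 20 patients move, and ACM:CM becomes 114:23, 119:18 or 129:8.

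**5. MCL-1, as a secondary check.** Assumptions: the same logistic slope per MCL-1 point in both groups (0.02 to 0.05); scores uniform over 30–70; and 28 of 109 ACM patients uniform over 0–30, which supposes 14 patients in each of the two lowest exploratory arms. Simulated AUC is 0.57 to 0.66 for scores of 30 or more, and 0.61 to 0.73 for the mixed ACM group. By-arm AUCs can therefore differ when the MCL-1 effect is identical, because the score ranges differ.

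**The case against.** **Membership is not layout.** Section 11.3 says who is in the set and how treatment is labelled. It does not say that all cohorts share one column. The protocol calls the other cohorts arms too, SAP 7.1 lets populations be subdivided, and SAP 4.2 judges relapsed/refractory safety relative to CM. So it goes too far to say that the plan states an intention to pool. But no passage calls for separate safety columns by cohort, and the table templates in SAP Appendix 2 have ACM and CM columns with no split by stage. The stated rule, followed literally, pools.

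**The consequence is limited.** Safety is descriptive, the templates drop p-values for safety data, and patient listings would allow Stage 2 tables later. This is correct and bears on severity. It does not make the default table interpretable. SAP 7 bars non-Stage 2 data from statistical inference, but descriptive safety tables fall outside that.

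**Some of the 81 are comparable.** Stage 1 and the 30 to <40% arm fit the current relapsed/refractory criterion of at least 30%. This stands, but those patients were still not randomised.

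**The SAP settles it.** A reader might infer that the SAP confines ITT, and so safety, to randomised patients. It does not do so cleanly: SAP 7.1 uses ITT for Stage 1 and exploratory summaries and treats newly diagnosed patients as ITT members. It was also written for Amendment 7, while the protocol describes Amendment 11.

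**MCL-1.** A reader might infer that by-arm AUCs are offered as randomised comparisons and will make MCL-1 look more predictive under ACM. The documents do not support that. Each AUC is a within-arm description, and SAP 7.10 already limits the analysis to relapsed/refractory ACM patients. A wide score range is legitimate there. With 28 CM patients and an AUC of 0.62, the standard error is about 0.12 (95% interval about ±0.23), larger than the illustrated shift. What remains is a conflict between the two documents.

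**Conclusion.** The point holds for safety. As written, the protocol's definitions give about 109 ACM patients, 81 of them (74%) never randomised, against 28 CM, with no limit to Stage 2 for the ACM-versus-CM summaries. These are planned counts, with everyone dosed and no crossover; crossover would widen the imbalance. The make-up of the exploratory arms is taken from the SAP synopsis.

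A reader might go on to infer that alvocidib's toxicity will be understated, or overstated, by a given amount. The documents do not support that. The event rates above are assumed, the net direction is unknown, and the figures show only that a distortion of several points is possible either way. Primary efficacy is not affected.

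This should be corrected before the safety tables are programmed. The MCL-1 and ITT wording conflicts are secondary.

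**What to change.** 1. In Protocol 11.3 and 11.4.4, and in the SAP safety sections, state that every ACM-versus-CM safety table (TEAEs, SAEs, 30- and 60-day mortality, TLS, laboratory results, vital signs) uses only randomised, treated Stage 2 patients.
2. Keep CM crossover patients in CM, as SAP 7.1 does, and show data after crossover separately. Without this, a Stage 2 restriction alone would still leave the any-time rule moving CM patients into ACM.
3. Give Stage 1, the relapsed/refractory exploratory arms and the newly diagnosed arm their own columns. Keep pooled ACM as a descriptive column only.
4. Align Protocol 11.4.3 with SAP 7.10. Limit any between-arm MCL-1 model or AUC comparison to Stage 2 patients, and keep the full-range analysis as ACM-only, relapsed/refractory only.
5. Reconcile the SAP's randomised-only ITT wording with its own use of ITT for Stage 1 and the exploratory arms.

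The cost is wording in both documents and extra table columns. No data collection changes, and no safety data are lost.

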4.5.3 Treatment Schema

4.5.3.1 Stage 1: Treatment with ACM over Days 1-9

Patients enrolled in Stage 1 will receive treatment with ACM as outlined below:

- **Days 1, 2 and 3: alvocidib (A) - Administer Daily**
30 mg/m² as a 30-minute (± 10 minutes) intravenous (IV) bolus
followed by
60 mg/m² over 4 hours (± 15 minutes) as an IV infusion
- **Days 4 and 5: Rest (no chemotherapy treatment)**
- **Days 6, 7, and 8: cytarabine (C) - Continuous over 72 hours**
2 gm/m² by continuous IV infusion over 72 hours (± 2.5 hours)
(ie, 667 mg/m² daily for total of 2 gm/m²)
- **Day 9: mitoxantrone hydrochloride (M) is administered 12 hours after completion of cytarabine treatment**
40 mg/m² by IV infusion over 1-2 hours (± 10 minutes)

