4.5.3.4 Crossover (Stage 2)

- Patients randomized to CM with progressive disease or no response after one cycle of CM may cross over to receive ACM.
- Patients randomized to CM with a best response of PR after 2 cycles of CM may also cross over to receive ACM.

- Continued use of mitoxantrone is optional after completion of one cycle of ACM
- Mitoxantrone must be omitted from subsequent cycles if the patient's lifetime daunorubicin equivalent exceeds 460 mg/m² (see *Appendix G* for conversion table) or the left ventricular ejection fraction (LVEF) drops below 45%. Patients crossing over who meet the above criteria will receive only AC (alvocidib and cytarabine) for all cycles instead of ACM.
- Patients who cross over to ACM may receive up to a combined total (CM + ACM) of 4 cycles.

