11.4.3 Pharmacodynamic Endpoint Analyses

Summary of baseline biomarker values will include within- and between-treatment-arm descriptive statistics. A logistic regression model will be fit to examine the relationship between baseline MCL-1 dependence and the independent binary variable achievement of CR during the study. The full model will include effects for baseline MCL-1 dependence, treatment arm, and the two-way interaction between baseline MCL-1 dependence and treatment arm. In addition, area under the curve (AUC) and 95% CI will be calculated (by treatment

arm) for the trapezoidal receiver operating characteristic curve. This value will quantify the ability of MCL-1 dependence to predict CR.

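### Protocol 11.3 analyses every CM patient who crosses over as ACM, SAP 7.1 keeps them in CM, and neither adverse-event window stops at crossover

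*Protocol*

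**What the plan says.** - **Protocol 11.3, safety set.** Treatment received is ACM "if alvocidib is administered at any time during the study. The safety patient population is the analysis population" for all safety data.
- **Protocol 11.3, per-protocol and response-assessment sets.** Treatment received is ACM "if alvocidib is administered at any time prior to CR (or at any time during the study for patients never achieving CR"). Neither rule mentions crossover. The section adds: "The response-assessment population is the primary population for assessing the correlation between MCL-1 dependency and response to ACM".
- **Protocol 11.4.3.** The MCL-1 model uses "achievement of CR during the study", with terms for treatment arm and the MCL-1-by-arm interaction.
- **Protocol 4.5.3.4.** "Patients randomized to CM with progressive disease or no response after one cycle of CM may cross over to receive ACM". The other route is a best response of PR after two CM cycles. Patients past the cumulative anthracycline or LVEF limit get alvocidib and cytarabine only (AC).
- **SAP 7.1.** The same three kinds of set carry an exception for ACM given to a crossover patient, and a separate crossover population is defined. SAP 7.10 leaves patients who received CM in cycle 1 out of its biomarker analysis. SAP section 4 names Amendment 7 as current, whereas Protocol 2.7 describes Amendment 11.
- **AE window, Protocol 11.4.4 and SAP 7.11.2.** A TEAE starts or worsens "any time after the first administration of any study drug up to 30 days following the last administration of any study drug". SAP section 3 lists alvocidib as a study drug.
- **Early mortality, Protocol 11.4.4.** "Estimates of 30- and 60-day mortality and their pointwise 95% CIs will be derived from Kaplan-Meier curves for OS by treatment arm".

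**The concern.** The two documents put the same patients in different columns, and neither says which rule governs. The protocol rule moves a group selected for failing CM into ACM, and their CM-cycle AEs go with them. The SAP rule avoids that, but because its AE window runs on to 30 days after the last dose of any study drug, AEs that occur on alvocidib are counted under CM.

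At stake are the AE tables, the supportive per-protocol and response-set analyses, the protocol's MCL-1 analysis and possibly early mortality. If the rule stays open until the data are in, it could be chosen with the results in view.

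**Working it through.** **Who is regrouped.** Crossover requires progression or no response after one CM cycle, or no better than PR after two. No such patient has had a CR before alvocidib. Any CR reached later comes after alvocidib, and without one the 'at any time' clause applies. Every crossover patient in the three protocol sets is therefore ACM.

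**Gap in the SAP exception.** It names ACM, but some crossover patients receive AC. By Appendix G, one 40 mg/m² mitoxantrone dose is 40 × 4 = 160 mg/m² daunorubicin equivalents. Entry allows up to 360, and mitoxantrone is dropped above 460. A patient who enters above 300 passes 460 after one CM cycle (300 + 160 = 460).

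**Inputs.** From Protocol 11.2.2: 28 per arm and CR of 70% vs 30%. The 28 reproduces with unpooled variance: (1.960 + 1.282)² × (0.21 + 0.21) / 0.40² = 27.6, so 28. The number of crossovers x is not given; I assume 3.5, 7 or 10.5 (12.5%, 25% or 37.5% of CM).

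**Supportive cycle-1 CR, protocol rule.** ACM = 19.6/(28 + x); CM = 8.4/(28 − x).

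| x | ACM | CM |
|---|---|---|
| 3.5 | 62% | 34% |
| 7 | 56% | 40% |
| 10.5 | 51% | 48% |

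At x = 14 the order reverses: 19.6/42 = 46.7% vs 8.4/14 = 60.0%. Under the SAP rule it stays 70% vs 30%.

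**AE rates.** Let pA and pC be the one-cycle risks on ACM and CM, independent within a patient, and u = 1 − (1 − pA)(1 − pC). Protocol gap = (28pA + x·u)/(28 + x) − pC. SAP gap = pA − [(28 − x)pC + x·u]/28. Take pA = 11% (grade 3 or higher GI events on ACM in newly diagnosed patients, Protocol 2.6.3) and assume pC = 5%. Then u = 15.45% and the true gap is 6.0 points.

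| x | Protocol gap | SAP gap | Ratio |
|---|---|---|---|
| 3.5 | 6.5 | 4.7 | 1.4 |
| 7 | 6.9 | 3.4 | 2.0 |
| 10.5 | 7.2 | 2.1 | 3.5 |

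With pC = 9% (the 7&3 figure) and x = 7, the true gap is 2.0, the protocol gap 3.6 and the SAP gap −0.5.

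**Window length.** Protocol 4.5.3.1 sets "Treatment with ACM over Days 1-9"; CM runs over Days 1–4. A one-cycle CM patient's window ends at Day 4 + 30 = 34. One who starts a cycle of crossover ACM at Day 45 has a last dose at Day 53 and stays in the SAP's CM column to Day 83, 83/34 = 2.4 times as long.

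**MCL-1 analysis, protocol rule, x = 7.** CM failures are 7/35 = 20% of the Stage 2 ACM group, 7/(35 + 25) = 12% with Stage 1 included, and 7/(60 + 56) = 6% with the exploratory arms as well.

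**Early mortality, if grouped by treatment received, x = 7.** With true mortality m in both arms and d deaths among crossover patients by that day, the protocol rule gives (28m + d)/35 vs (28m − d)/21. At Day 30, m = 5% (1.4 deaths per arm) and d = 0 give 4.0% vs 6.7%. At Day 60, m = 10% gives 8.0% vs 13.3% (d = 0), 10% vs 10% (d = 0.7) or 10.9% vs 8.6% (d = 1). The 5% and 10% are ACM treatment-related mortality in Protocol 2.6.3, used as assumptions.

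**The case against.** The strongest reply is that Protocol section 11 is an overview that defers detail to the SAP, and the SAP already has the exception, a crossover population and a cycle-1 CR endpoint. That settles less than it seems. The SAP is keyed to Amendment 7, its exception does not clearly reach AC patients, and its AE window creates the opposite misattribution. It allows AE summaries in subsets but, in the text available, commits to none for crossover patients. Table 9 lists suggested titles only.

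Several limits do stand:
- A reader might infer that the AE gap always doubles. The ratio depends on uptake and on the assumed rates. The true gap used here covers one cycle, whereas responders in either arm may have up to four, which also lengthens ACM windows.
- A reader might infer that early mortality is certainly biased in favour of ACM. The mortality wording says by treatment arm, which could mean randomized arm. Protocol 11.3 points to treatment received for all safety analyses, but the text is mixed. Day 30 rests on very few deaths, and at Day 60 the bias can go either way or vanish.
- The 20% share in the MCL-1 analysis holds for Stage 2 alone. Protocol 11.4.3 does not restrict the analysis to Stage 2.
- Removing CM patients from the 11.4.3 model altogether would leave its arm and interaction terms inestimable.
- A cycle-1-only AE comparison with fixed day limits would be a new estimand. Resolving the conflict does not require it.

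**Conclusion.** The conflict is real and should be settled before database lock. It follows from the text alone: the protocol counts all crossover patients in these sets as ACM, the SAP leaves them in CM (unclear for AC), and each rule credits one regimen with the other's AEs.

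The sizes are illustrations that rest on assumed uptake, assumed CM risks and independence. At 11% vs 5%, the protocol-rule AE gap is 1.4 to 3.5 times the SAP-rule gap over the uptake range, and supportive CR shrinks from a 40-point difference to between 28 and 3 points under the protocol rule.

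A reader might infer that the main result is at risk. It is not: both documents analyse the primary cycle-1 CR test in the ITT set by randomized arm. Nor does the point extend to TLS, laboratory or vital-sign summaries, since the SAP plans a cycle-1 TLS table, a 7-day laboratory TLS window and by-cycle laboratory and vital-sign results.

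**What to change.** 1. In Protocol 11.3 and SAP 7.1, for the safety, per-protocol and response sets, write: *Treatment received is the regimen administered in cycle 1; alvocidib given after crossover (as ACM or AC) does not change a patient's group.*
2. In Protocol 11.4.3, use cycle-1 CR. Keep the two-arm model with its interaction, with crossover patients in CM. Leave out patients who received CM in cycle 1 only from a separate ACM-only analysis, as SAP 7.10 does.
3. In Protocol 11.4.4 and SAP 7.11.2, end a CM patient's AE window at the earlier of the first alvocidib dose and 30 days after the last CM dose before it. Show exposure time. Report AEs after the first alvocidib dose separately for the crossover population that SAP 7.1 defines.
4. Group the 30- and 60-day mortality table by the same rule and footnote deaths after crossover.

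The cost is wording plus a few AE tables; dose dates and AE start and stop dates are already collected. There are two drawbacks. CM follow-up in the AE tables becomes shorter. AEs that start on CM and worsen after crossover cannot be split by grade, because Protocol 8.4 records only the highest grade with overall dates.
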